The risks of this research are consistent with the risks that a normal child would experience as a part of their daily life. The risks associated with wearing the actigraph are no greater than those associated with wearing a wristwatch. However, there are three sources of potential risk in this study. First, there is the safety risk of the child coming to the laboratory for assessments. Second, there is a risk that parents may experience some distress while answering some of the survey questions related to parental or child behavior. It is also possible that children may express discomfort from the study activities. Third, there is a risk of potential loss of confidentiality. We are unaware of any risks associated with the collection of saliva using our published methods. I will use standard procedures, which I have refined during more than 75 circadian assessments with young children over the past six years.

12.2 Discuss what steps will be taken to minimize risks to subjects/data.

Although the risks involved in each of the study procedures are minimal, we will take necessary precautions to minimize the risks to the greatest extent possible.

Safety of child participants in the laboratory: Researchers will be with subjects at all times during in-lab data collection, and at least one parent/guardian must be present throughout all laboratory visits. All researchers and student research assistants must pass a comprehensive background check and obtain a fingerprint clearance card from the Arizona Department of Public Safety before interacting with subjects or families. There is also the risk that the parent may disclose, or study staff may observe, instances of child maltreatment that must be reported to child protective authorities. Parents will be informed of this and other potential risks during the informed consent process.

Comfort of child participants during study activities: It is up to the parent to determine whether they would like to keep trying to encourage their child to complete the activity, but we will never force a child to continue with a study activity against their will. If the child is expressing clear discomfort with a study activity, the study team will pause the activity and give the child a break and discuss with the parent. At the parent's request we will try to engage the child in the study activity again. If they continue to express discomfort, then the study team will stop the study activity. During the in-lab salivary assessment, this may mean skipping the currently scheduled saliva sample and coming back to the child in 20-30 minutes to see if they are willing to try the next sample. Because we are keeping kids up past their bedtime for the two salary melatonin assessments, they can sometimes get overtired and cranky. We find that a little break and encouragement from the parent or a snack often allows the child to reset and finish the assessment.

Parental distress when completing questionnaires: This distress would be expected to be only transient, and parents will be reminded that they can skip any question they do not feel comfortable answering.

Maintaining participant confidentiality: Children will be assigned ID numbers upon enrollment in the study and these numbers will be used in all data records. Parent contact information, signed consent forms, and the code to match ID numbers to participants will be kept separately in a secure location in the locked laboratory. All data records will be maintained on password protected computers in the Sleep and Development Laboratory, only accessible to the appropriate study researchers.

Participants will be informed that they can withdraw from the study at any time and will receive pro-rated compensation.

13.0 Costs, Compensation, and Injury:

13.1 Describe any costs, monetary and non-monetary, that subjects may incur. This includes time.

There are no costs to subjects except for their time.

13.2 Discuss the amount of compensation (monetary and/or non-monetary) subjects may receive. Describe if compensation will be prorated.

For completing the study protocol, families are compensated a total of \$400. Children receive small non-monetary gifts for completing each circadian assessment. For any family who chooses to terminate study participation, compensation will be pro-rated as follows:

Baseline:

Completing online surveys: \$20

Actigraphy: \$40

In-lab phase assessment: \$80

Intervention:

\$50/week for 2 weeks

Post-Intervention:

Completing online surveys: \$20

Actigraphy: \$40

In-lab phase assessment: \$80

Completing qualitative interview: \$20

The breakdown of the pro-rated compensation will be discussed with parents during consent. This study requires a significant amount of work and time on the part of parents. Thus, we believe this compensation structure and amount are consistent with the effort of participating families, but not so high as to be coercive.

14.0 Privacy of Subjects and Confidentiality of Data:

14.1 Describe steps, if any, to protect the privacy of the subjects throughout their participation (e.g., during the recruitment process, consent process, and/or research procedures).

Consenting and all lab-based assessments (e.g., training visits, pupillometry, DLMO) will occur privately in designated lab space in UAHS or in the UAHS Center for Sleep, Circadian, and Neurosciences Research behind closed doors with no windows conveying into the room. All other research activities will occur at the subject's homes.

14.2 Will data/specimens be kept for future research, including unspecified future research and genetics? Yes No

14.3 If yes to the above question, describe future use plans here, including unspecified research, any storage in a repository (if applicable), and what data will be retained/reused.

No specimens or identifiable data will be kept. Only fully unidentified data will be kept indefinitely by the PI for future, unspecified research. De-identified data will also be deposited into the National Sleep Research Resource repository.

14.4 Discuss how study results will be shared with subjects, families, and/or the institution, both immediately and long-term.

Parents will have the opportunity to review their child's actigraphy and melatonin data with the researchers after completion of the study and melatonin assays.

14.5 Indicate if the research team will be accessing any of the following records.

 Substance abuse records (HIPAA and 42 CFR Part 2)
 Medical records (HIPAA)
 Educational records (FERPA)*
 Employee records (ABOR Policy 6-912)*
 Other, specify: Click or tap here to enter text.

14.6 For each record source selected above, list the data elements to be accessed, who will access them, and how the information will be obtained.

N/A

14.7 Indicate where data will be stored:

 Box@UA	 OnCore
 Box@UA Health	 PACS medical imaging software
 Clinical Data Warehouse (CDW)	 Password Protected Drive
 Cloud Server	 REDCap
 Department Drive	 Transmitting/receiving subject data to/from an outside group
 Department Office	 UA Records Management & Archives
 Encrypted Drive	 Banner Server/Platform, specify:
 External Drive (hard drive, USB, disk)	 Soteria
 Google Suite for Education	
 HIPAA Research Computing Service	 Other, specify: Click or tap here to enter text.

14.8 For EACH of the storage locations checked above, discuss the type of data to be stored, including if the data will be identifiable, coded, or de-identified upon storage.

If data will be coded, specify who will maintain the code, where it will be stored, and when it will be destroyed. If data will be de-identified, explain if there is any possibility that the data could be re-identified.

All signed paper consent forms and media authorization forms will be stored in separate binders in [name] locked office.

All electronic data will be stored on an encrypted server only accessible to authorized personnel. The data will be stored indefinitely. Information about the data may be shared with the University of Arizona Institutional Review Board, the Office for Human Research Protections and other federal or state regulatory agencies. No external third parties will have access to the data.

- REDCap: All questionnaire data will be obtained and initially stored using REDCAP. This will include identifiable and coded data.

-Box Health: Will be used to store identifiable and coded information collected. Copies of raw data from the REDCap questionnaires will be later downloaded and stored in Box Health. Only the Principal Investigator, Co-Investigator, and relevant research assistants may access records stored in the Box Health drive. Photographs taken of participants will be stored in Box Health by coded number. The study code will be stored on a password-protected excel file in Box Health, maintained by the PI, and will be destroyed upon completion of data analysis. We will also keep a separate list of ineligible subject's names to avoid recontact, which will be deleted upon completion of data collection.

De-identified or coded data will also be stored in OnCore per UAHS policy.

De-identified data will also be deposited into the National Sleep Research Resource repository.

14.9 If collecting biological specimens, please describe the storage location for the specimens, including if they will be identifiable, coded, or de-identified upon storage.

Saliva samples will be stored in a minus 80-degree freezer in a locked laboratory in the UAHS Center for Sleep, Circadian, and Neurosciences Research (UAHS 0418) immediately after data collection. They will then be transferred to the University of Arizona Biorepository for long-term storage before being shipped out for assaying. Saliva samples will be labeled with participant's ID number, the date collected, and sample number. Samples will not be labeled with any identifiable information.

14.10 Storage of research records (research records should be maintained for whichever of the following time periods is the longest, select one):

 I will store research records for at least 6 years past the time the study is concluded.
 For studies involving minors, I will store research records for at least 6 years after the youngest participant turns 18.
 I will store research records for the length of time required by law or study sponsor, please specify: Click or tap here to enter text.

14.11 Describe what security controls (e.g., administrative, physical, technical) are in place to make sure data/specimens are secure.

Names, contact information, and any identifiable information from the subject will be kept separately from the subject's data records. All electronic data is stored on password protected computers that are only accessible by authorized study personnel. Saliva samples will be labeled only with the participant ID number and data collected and stored in a locked laboratory.

REDCap is a secure, web-based application designed to support data capture and storage for research studies, providing: 1) an intuitive interface for validated data entry; 2) audit trails for tracking data manipulation and export procedures; 3) automated export procedures for seamless data downloads to common statistical packages; and 4) procedures for importing data from external sources. REDCap has been designed to allow for compliance with such standards as HIPAA, 21 CFR Part 11, FISMA (low, moderate, high), and international standards. Also included are a built-in project calendar, a scheduling module, ad hoc reporting tools, and advanced features, such as branching logic, file uploading, and calculated fields. The University of Arizona is an institutional member with a Bioinformatics Manager in the CaTS Research Center responsible for development and maintenance. This application will be used in the development of electronic forms for data collection to be used by study staff.

14.12 Indicate how data/specimens will be shared with collaborating entities:

 Data and/or specimens will not be shared between UA and any outside group or collaborating entity.
 Data/or specimens will be transmitted and/or disclosed to an outside group or a collaborating entity.
 Data and/or specimens will be received from an outside group or a collaborating entity.
 PHI will be transmitted to or received from an outside group or a collaborating entity. *
 A Limited Data Set will be transmitted or received from an outside group or a collaborating entity. *
 Data/specimens will be sold to pharmaceutical companies.

14.13 Describe what information will be shared, who it will be shared with, and how it will be shared (e.g., secure file transfer, REDCap, etc.). Also include information about future use sharing and repositories. Specify if the shared data will be identifiable, coded, a limited data set, or de-identified.

De-identified data will be deposited into the National Sleep Research Resource repository.

Coded samples will be sent to Solid Phase Inc. for assaying. Solid Phase Inc will provide the assay results back to the UA study team.

15.0 Additional Questions (complete as applicable):

15.1 Subject Injury: If the research involves more than minimal risk to subjects, describe the provisions for medical care and available compensation in the event of research related injury. If the Human Research has a clinical trial agreement, this language should reflect what is stated in the agreement.

N/A

15.2 Withdrawal of Subjects: Discuss how, when, and why subjects may be removed from the study. If abrupt withdrawal is necessary, discuss how subjects will be withdrawn so that they are not put at increased risk. Discuss what happens if a subject is withdrawn from one part of the study but asked to continue with other parts, such as ongoing follow-up.

Because salivary melatonin is a main measure of the study, participants may be removed if it becomes evident during the training visits that they are not able to provide adequate saliva for samples. Subjects may also be removed from the study for consistently failing to complete study activities (e.g., not wearing the actiwatch or completing the sleep diaries). Any subject withdrawn from the study will receive pro-rated compensation commensurate with the sections of the study already completed.

15.3 Monitoring for Subject Safety: Provide a brief lay discussion of your plan to monitor for subject safety. Describe what safety information will be collected, including serious adverse events, how safety information will be collected, and the frequency of collection including a timeline of when the data and review(s) will occur, who will review the information, and the plan for reporting findings.

If there will not be a way to monitor for subject safety, please explain.

All adverse events will be recorded and reported to the IRB. Participants will have access to a phone number and email address through which to contact study personnel and in the case of any emergencies.

15.4 Data Management Plan: Please discuss the data management plan, if required by your funder. For additional resources, reference the HSPP [Data Management webpage](#). If your sponsor/funding agency requires a Data Management Plan, please upload the approved copy in eIRB. This section and the informed consent form should contain all pertinent information including:

- What data/metadata will be shared (imaging, survey; raw data or derived; protocol, data form; etc.)
- What repository will be used (if known)
- How will data be stored (in a de-identified or identifiable format)

De-identified data will also be deposited into the National Sleep Research Resource repository. Appropriate measures such as assigning each participant a unique code will be used for data de-identification and sharing. The final dataset will consist of demographics, sleep behavior collected through parent-report questionnaires (Children's Sleep-Wake Scale, Children's Sleep Habits Questionnaire, and Children's Chronotype Questionnaire), sleep timing and light history assessed through wrist actigraphy, salivary melatonin, and pupillometry from 60 children ages 5.0-6.9 years with parent-reported sleep-onset difficulties.

The University of Arizona will assure the timely release and sharing of appropriate data no later than the acceptance for publication of the main findings from the final dataset. The duration of preservation and sharing of the data will be a minimum of 10 years after the funding period.

15.5 International Research: Describe site-specific regulations or customs affecting the research, local scientific and/or ethical review structures that differ, and if community advisory boards are involved. If so, describe their composition and involvement. For research being conducted outside of the US, please explain any local laws, regulations, or customs the IRB needs to be aware of.

N/A

Additional items needed for review:

- Word versions of applicable subject materials: Consent Forms, Recruitment Materials, Data Collection Materials, Participant Materials
- Current PI CV or biosketch
- Advisor approval (if the PI is a student or medical resident)
- Department/Center/Section Review approval
- [Scientific/Scholarly review](#) approval
- Responsible physician approval and CV (if the PI is conducting medical procedures for which he/she is not clinically certified to perform)

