Describe the purpose, specific aims, objectives, questions to be answered, hypotheses, and/or primary and secondary study endpoints of this Human Research protocol.

The overall goal of this research is to test the feasibility and preliminary effectiveness of two proposed light-related intervention components to advance sleep and circadian timing in order to improve sleep quality in early childhood. After baseline assessments of circadian timing (salivary DLMO), sleep timing (actigraphy), and parent-reported sleep quality and behaviors, children (5.0-6.9 years) will be randomly assigned to one of three 2-week interventions: (1) adjustment of home lighting environment (implementation of smart lightbulbs to reduce intensity and blue-light 1 h before bedtime); (2) reduction in evening light exposure (amber-tinted glasses 1 h before bedtime^{47, 48}); or (3) a sham intervention (clear glasses 1 h before bedtime). Post-intervention, a secondary assessment of all outcomes will be performed, as well as qualitative interviews with parents. With these data, we will address the following specific aims:

Aim 1: To determine feasibility and acceptability of two different potential components of a circadian health intervention in young children. We hypothesize that adjustment to home lighting environment and reduction in evening light exposure will both be perceived by parents and children as feasible and acceptable intervention strategies, as measured through compliance rates and qualitative post-intervention interviews with parents.

Aim 2: To examine the preliminary effectiveness of two different potential components of a circadian health intervention on sleep and circadian timing, sleep quality, and parent-reported sleep behaviors in young children. We hypothesize that adjustment to home lighting environment and reduction in evening light exposure will both result in an earlier DLMO and earlier sleep onset, compared to sham intervention.

Exploratory Aim 3: To examine individual differences in photosensitivity in young children. We hypothesize that individual differences in photosensitivity assessed through pupillometry will moderate the effects of the interventions on DLMO and sleep onset.

4.0 Funding Information:

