 Adults unable to consent (i.e., cognitively impaired adults) *	

6.2 For each of the above selected categories, describe the inclusion and exclusion criteria. Indicate age range, gender, and ethnicity.

Inclusion requires that children are aged 5.0-6.9 years at the time of enrollment with a parent-reported sleep onset of \geq 60 min after parents' desired bedtime at least three nights per week. Equal numbers of boys and girls will be enrolled. Children are *excluded* for the following reasons:

- All sleep disorders as indicated on the telephone screener or by clinical cut-off scores on the Children's Sleep Habits Questionnaire (CSHQ),^{49, 50} except for insomnia or DSWPD⁵¹ as features of these disorders are directly targeted by the intervention. Secondary analyses will explore if outcomes differ among participants with or without parent-reported symptoms consistent with these diagnoses.
- Physical abilities that interfere with assessments (e.g., visual impairment), developmental disabilities (e.g., autism, attention-deficit/hyperactivity disorder (ADHD), pervasive developmental disorder), epilepsy or other neurological disorders, metabolic disorders, medical conditions that commonly require treatments or assessments during the night (e.g., cancer, diabetes, active asthma), current infection or lead poisoning; a head injury involving loss of consciousness in the past 6 months.
- Current use of medications affecting daytime sleepiness, the circadian system, or light sensitivity.
- Eye disorders or color blindness (determined with Ishihara Color Vision Test); corrected vision with eyeglasses is permitted.

One adult parent of each participating child will also take part in the study. Parents must be able to provide consent and to complete the interview at the end of the study.

6.3 Describe the total number of subjects to be enrolled locally under this IRB approval. If obtaining specimens, specify the maximum number of specimens needed for this project.

We expect to enroll 60 children and 60 parents. We will aim to enroll 30 girls and 30 boys. Each child will provide a total of 24 saliva samples across the research protocol, for a total number of 1,440 samples expected to be collected as part of this project.

7.0 Recruitment Methods:

7.1 Select the methods used to recruit individuals.

 Email	 Screening of the Electronic Medical Record (EMR)

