8.0 Diversity, Equity, and Inclusion

8.1 Explain how the research plan (recruitment, study population, data collection, etc.) is equitable and represents the demographic makeup for the location in which the research will be conducted.

Subjects will be recruited through flyers from within a 60-mile radius around The University of Arizona, as well as outreach at local community events and festivals. We will enroll an even number of male and female child participants. No child will be excluded from the study based on sex, race, ethnicity, or any other demographic characteristic.

8.2 Describe whether non-English speaking subjects will be included in the study. If yes, please explain how your research team is prepared to meet the needs of the population. If not, please explain why non-English speakers will be excluded from the study population.

As an early career PI, [name] will be the one consenting all participants and overseeing data collection and is not fluent in any other language. Non-English speaking subjects will not be included in the study because [name] would have no way of ensuring that they understood all aspects of the protocol and all of their questions were answered satisfactorily.

8.3 What methods will you use to collect demographic information from participants? If you will not collect demographic information, please explain why not.

Demographic information will be collected from participants via a Redcap questionnaire.

9.0 Consenting Process:

9.1 Indicate the informed consent process(es) and/or document(s) for the study. Check all that apply.

Written Consent
 Informed Consent (ICF) – written or electronically signed form
 Parental Permission – written or electronically signed form
 Assent (participants under 18) – written or electronically signed form

 Combined ICF/PHI Authorization – written or electronically signed form
 Standalone Protected Health Information (PHI) HIPAA Authorization – written or electronically signed
 Translated Consent/Assent – written or electronically signed form(s)
 Short Consent Form – written or electronically signed form (see guidance on Short Form process)
 Debriefing Script or Form – document used to properly inform subjects of the study's purpose when intentionally deceived

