Pre-assessment: During the initial phase of the study (pre-assessment), participants will come to the lab for 3 training visits to familiarize the child with the researchers, measure photosensitivity (pupillometry), cognitive performance (NIH Toolbox), and to introduce them to the saliva collection technique.

Baseline assessment: After the first pre-assessment visit, there will be a two-week at-home baseline assessment. Pre-intervention data will be collected on sleep timing (actigraphy), parent-reported sleep timing and behavioral sleep quality, light exposure (actigraph), and a baseline assessment of circadian timing (salivary DLMO). During 7 of the days (chosen by the subjects), parents will be asked to complete a daily diary of their child's screen media use. The second and third pre-assessment visits will occur during the baseline assessment period.

Randomization: Children will be randomly assigned to one of three two-week interventions (adjustment to home lighting, amber-tinted glasses, or clear glasses). Children will be randomized to the three conditions in a 2:2:1 ratio, stratified by sex. For each participant enrolled, a random number generator will provide a number from 1-30, which corresponds to an intervention condition for each sex.

Intervention Period: Changes in sleep timing and light exposure will be assessed throughout the intervention period via actigraphy, light sensing, and sleep diaries. Parents in the amber-tinted or clear glasses arms will also complete a daily diary detailing when the glasses are worn.

Post-intervention: After the intervention is complete, a secondary assessment of sleep timing via actigraphy (one week), light exposure, parent-reported questionnaires, cognitive performance, media diaries, and DLMO will be performed, as well as qualitative interviews with parents to assess child and family experiences. Interviews will not be audio- or video-recorded.

Throughout the duration of the study, the child will wear a wrist actigraph to record sleep timing and light history. Parents will complete a daily sleep diary, which documents children's sleep schedules and nocturnal awakenings.

5.A. Interventions

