Adjustment to Home Lighting. The presence of more blue light in the home is associated with later circadian timing in both school-aged children and adults.⁵² This intervention will adjust the evening home lighting environment to be less stimulating to children's circadian clocks. Researchers will visit the participant's home to install smart light bulbs. Smart light bulbs (WYZE, dimmable and color tunable LED bulbs with CCT range of 2700K – 6500K) will be installed in participants' homes light fixtures (in the child's bedroom, bathroom, as well as areas the child is likely to spend time in after dinner (i.e., living room, playroom)). The researchers will program the lights to transition to a lower CCT and dimmer intensity to achieve the recommended evening mEDI of 10 lux⁵³ starting 1 h before the child's parent-selected bedtime.

Amber-Tinted Glasses. Wearing "blue-blocker" glasses (lenses that filter out the blue portion of the visible spectrum) can reduce the melatonin suppression and alertness effects of evening light exposure in both adults⁴⁸ and adolescents,⁵⁴ as well as advance the timing of the circadian clock and sleep onset,⁵⁵ compared with participants wearing placebo lenses. This intervention will examine their efficacy in advancing young children's sleep and circadian timing. Children will be given a pair of glasses (Block Blue Light), with amber-tinted lenses (advertised as blocking

100% of light from 380-550 nm;⁵⁶ reduction in mEDI measured as 96.5%. The glasses being used in this study are specifically designed and marketed for children to block blue light. They are commercially available devices that will be used how they are supposed to be used. Link: <https://www.blockbluelight.co.nz/collections/kids-blue-light-glasses/products/kids-blue-blocking-glasses-pink>. Children will wear the glasses starting 1 h before parent's selected bedtime. A small temperature sensor is placed on the inside of the glasses to objectively determine when children are wearing them. Parents will also complete a daily diary detailing when the glasses are worn.

Sham Intervention (clear glasses). The sham intervention consists of the same protocols for the amber-tinted glasses, except that children will be asked to wear a pair of glasses with clear lenses (advertised as blocking 50% of light from 400-500 nm; reduction in mEDI measured as only 16.7%, which are significantly less effective at blocking short-wavelength light).

5.B. Measures

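### Does drawing a number from 1 to 30 for each child put the 2:2:1 allocation at risk?

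*Protocol*

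**What the plan says.** The Randomization paragraph of protocol section 10.2 sets the ratio and the stratification: "Children will be randomized to the three conditions in a 2:2:1 ratio, stratified by sex". The next sentence gives the mechanism: "For each participant enrolled, a random number generator will provide a number from 1-30, which corresponds to an intervention condition for each sex". Neither sentence mentions single use of numbers, blocks, or a rule for a child beyond the 30th of one sex.

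Other sections bear on how this is read:

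- Section 6.3 expects 60 children and adds "We will aim to enroll 30 girls and 30 boys". Sections 6.2 and 8.1 state more firmly that the two sexes will be enrolled in equal numbers.
- Section 3.0 places assignment after baseline: "After baseline assessments of circadian timing (salivary DLMO), sleep timing (actigraphy), and parent-reported sleep quality and behaviors, children (5.0-6.9 years) will be randomly assigned".
- Section 15.2 allows early removal: "participants may be removed if it becomes evident during the training visits that they are not able to provide adequate saliva for samples".
- Section 15.4 describes the final dataset as including "pupillometry from 60 children ages 5.0-6.9 years with parent-reported sleep-onset difficulties".

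**The concern.** The protocol states both a target ratio and a mechanism, and the mechanism as worded does not guarantee the ratio. If the generator may return the same number twice, allocation is simple randomisation with probabilities 0.4, 0.4 and 0.2, and stratifying by sex balances nothing. If each number is used once, the scheme is in effect one block of 30 per sex. The ratio is then exact only when a sex reaches 30, and a 31st child has no number. Removals at the training visits make a count other than 30 conceivable.

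What is at stake is the sham arm. It is the smallest arm and the only comparator for both hypotheses of Aim 2, so a chance shortfall there would widen both contrasts together. Allocation also cannot be repaired once children are in the trial.

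**Working it through.** **Inputs.** Ratio 2:2:1 within sex and numbers 1 to 30 (section 10.2); 30 girls and 30 boys (section 6.3). The protocol gives no dropout rate, so every shortfall below is an assumption.

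**The plan's own figure.** 30 × 2/5 = 12, 30 × 2/5 = 12 and 30 × 1/5 = 6, so 12:12:6 per sex and 24:24:12 overall. Single-use slots at 30 + 30 give this exactly.

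**If numbers may repeat.** The sham count is Binomial(60, 0.2).

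- Mean 12; SD = √(60 × 0.2 × 0.8) = 3.1; central 95% range 6 to 18.
- P(8 or fewer sham) = 12.7%.
- P(3 or fewer sham in a given sex) = 12.3%, so for at least one sex 1 − (1 − 0.123)² = 23.0%.

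The standard error of an active-versus-sham contrast is proportional to √(1/active + 1/sham). At 24 against 12 this is √(1/24 + 1/12) = 0.354. Relative to that:

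| Active : sham | √(1/active + 1/sham) | Relative SE |
|---|---|---|
| 26 : 8 | 0.404 | +14% |
| 27 : 6 | 0.451 | +28% |
| 21 : 18 | 0.321 | −9% |

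Over all possible allocations of 60 children the loss averages about 2.6% (median 0.8%). The estimates remain unbiased.

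**If each number is used once and a sex falls short.** With n children of a sex, the sham count is Hypergeometric(30, 6, n), summed over the two sexes. Permuted blocks of 5 and 10 are the comparison.

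| Girls + boys (assumed) | P(8 or fewer sham), single-use | Same, blocks of 5 and 10 |
|---|---|---|
| 24 + 24 | 18.6% | 6.3% |
| 30 + 18 | 15.3% | 0.7% |
| 25 + 25 | 10.3% | 0.7% |
| 27 + 27 | 1.3% | 0.07% |

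These tail probabilities look larger than their consequence. At 48 children the exact split is 19.2:19.2:9.6, so 8 sham is already close to expectation. The relative SE at 20:20:8 is √(1/8 + 1/20) / √(1/9.6 + 1/19.2) = 0.418 / 0.395 = 1.06, a loss of about 6%. The average loss at 24 + 24 is about 0.6% with single-use slots and 0.2% with blocks, a difference of about 0.4 percentage points.

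**Cost of smaller blocks.** An observer who knows all earlier allocations in a sex, and the possible block sizes, guesses the next arm correctly about 58% of the time with blocks of 5 and 10. The figure is 50% with one single-use set of 30 and 40% with independent draws.

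**The case for a change.** The case for acting is that the protocol itself fixes the mechanism, so this is not a detail left to an analysis plan. Under independent draws a repeated number is more likely than not by the seventh child of a sex (53%). Staff would soon meet a repeat with no written rule, and an ad hoc choice to redraw is what a protocol should prevent. A clarifying sentence needs no extra children or visits.

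It is true that the rule is unwritten, and a sentence stating single use within sex would do no harm. The rest carries less weight. If repeats were intended, numbers 1 to 5 would serve as well, the choice of 30 would have no purpose, and stratification would have no effect. The wording therefore points to single-use slots, and the largest harms (6 to 18 sham, +28%) belong to the less likely reading. The 30 + 18 split and the 31st child both conflict with the equal-numbers statements in sections 6.2 and 8.1. Under section 3.0, children removed before the baseline assessments are complete would not yet have been assigned and would use no slot. A shortfall then also requires that they are not replaced, on which the protocol is silent. A thin sham group in one sex matters little because no aim concerns effects by sex.

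Permuted blocks would protect the ratio better under a shortfall, but predictability is a real cost here. The principal investigator "will be the one consenting all participants and overseeing data collection" (section 8.2), and researchers visit the participant's "home to install smart light bulbs" (section 5.A), so earlier allocations may be known to those who enrol.

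**Conclusion.** No change to the plan is needed. The text omits a rule that the team can fill sensibly: 30 single-use numbers per sex, assigned after baseline as section 3.0 says. On that reading the design gives exactly 24:24:12 at 30 + 30. On the other reading allocation is still valid, with an average precision loss of about 2.6% and a modest tail risk in the sham count.

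Moving to small blocks is a trade-off and not a correction: about 0.4 percentage points of average standard error at an assumed 48 children, against a rise in guessability from about 50% to 58%. The conclusion rests on single use being the intent, which is inferred from the match between 1 to 30 and the stratum size, and on enrolment staying near the stated equal numbers. A large shortfall, or strongly unequal numbers of girls and boys, would make blocks more attractive, but nothing in the protocol predicts either.
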